8.1.2. QTc Stopping Criteria

- The QTc is the QT interval corrected for heart rate according to Bazett's formula (QTcB), Fridericia's formula (QTcF), and/or another method, machine-read or manually over-read. The *same* QT correction formula *must* be used for *each individual participant* to determine eligibility for and discontinuation from the study. This formula may not be changed or substituted once the participant has been enrolled.
- For example, if a participant is eligible for the protocol based on QTcB, then QTcB must be used for discontinuation of this individual participant as well.
- Once the QT correction formula has been chosen for a participant's eligibility, the *same formula* must continue to be used for that participant *for all QTc data being collected for data analysis*. Safety ECGs and other non-protocol specified ECGs are an exception.

• The QTc should be based on single or averaged QTc values of triplicate electrocardiograms obtained over a brief (e.g., 5-10 minute) recording period.

A participant who meets the bulleted criteria based on the average of triplicate ECG readings will be withdrawn from study treatment:

- QTc >500 msec OR Uncorrected QT >600 msec
- Change from baseline of QTc >60 msec

For participants with underlying bundle branch block, follow the discontinuation criteria listed below:

- Baseline QTc with Bundle Branch Block <450 msec, Discontinuation QTc with Bundle Branch Block >500 msec
- Baseline QTc with Bundle Branch Block <450-480 msec, Discontinuation QTc with Bundle Branch Block ≥530 msec.

See the SoA for data to be collected at the time of early withdrawal (EW visit) and follow-up and for any further evaluations that need to be completed.

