- 6. **12-lead ECG assessment at Screening (Visit 1):** Site investigators will be provided with ECG over-read conducted by a centralized independent cardiologist, to assist in evaluation of subject eligibility. For this study, an abnormal and clinically significant ECG that would preclude a subject from entering the trial is defined as a 12-lead tracing that is interpreted as, but not limited to, any of the findings in Table 2:

Table 2 Abnormal and clinically significant ECG findings

- Sinus bradycardia <45bpm
- *Note: Sinus bradycardia <45bpm should be confirmed by two additional readings at least 5 minutes apart.
- Sinus tachycardia ≥110bpm
- *Note: Sinus tachycardia ≥110 should be confirmed by two additional readings at least 5 minutes apart.
- Multifocal atrial tachycardia (wandering atrial pacemaker with rate >100bpm)
- Evidence of Mobitz II second degree or third degree atrioventricular (AV) block
- Pathological Q waves (defined as wide [>0.04 seconds] and deep [>0.4mV (4mm with 10mm/mV setting)] or >25% of the height of the corresponding R wave, providing the R wave was >0.5mV [5mm with 10mm/mV setting], appearing in at least two contiguous leads.
- *Note: prior evidence (i.e., ECG obtained at least 12 months prior) of pathological Q waves that are unchanged are not exclusionary; and the investigator will determine if the subject is precluded from entering the study.
- Evidence of ventricular ectopic couplets, bigeminy, trigeminy or multifocal premature ventricular complexes.
- For subjects without complete right bundle branch block: QT interval corrected for heart rate by Fridericia's formula (QTc[F]) ≥450 msec or an ECG that is unsuitable for QT measurements (e.g., poor defined termination of the T wave).
- For subjects with complete right bundle branch block: QTc(F) ≥480 msec or an ECG that is unsuitable for QT measurements (e.g., poor defined termination of the T wave).
- *Note: All potentially exclusionary QT measurements should be confirmed by two additional readings at least 5 minutes apart.
- ST-T wave abnormalities (excluding non-specific ST-T wave abnormalities)
- *Note: prior evidence (i.e., ECG obtained at least 12 months prior) of ST-T waves that are unchanged are not exclusionary and the investigator will determine if the subject is precluded from entering the study.
- Clinically significant conduction abnormalities (e.g., Wolff-Parkinson-White

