8. DISCONTINUATION CRITERIA

8.1. Discontinuation of Study Treatment

Participants that permanently stop study treatment are encouraged to remain in the study. Participants have the right to discontinue study treatment before the end of the study. A participant may also be asked to discontinue study treatment at the Investigator's discretion.

Participants who withdraw from study treatment prematurely (for any reason) should, where possible, continue to be followed-up until the completion of the Safety Follow-up assessments:

• For participants who discontinue IP early, but have not withdrawn consent to participate in the study, an early withdrawal (EW) visit will be performed 4 weeks after the last dose of blinded study treatment. These participants should continue in the study and complete all assessments at the remaining protocol-defined visits until their EW visit. Participants should resume regular treatment for their asthma, as determined by the investigator. Three Follow-up visits will then be performed 4, 8, and 12 weeks after the EW visit for safety assessments.

CONFIDENTIAL

• Participants who discontinue IP early and withdraw consent to participate in the study should complete as many assessments planned for the EW visit as possible.

If this is not possible, the Investigator must encourage the participant to participate in as much of the study as they are willing (or able) to.

A participant may be withdrawn from study treatment at any time. A reason for premature discontinuation of study treatment (e.g., AE, lack of efficacy [including loss of asthma control], protocol deviation, Investigator discretion, consent withdrawn etc.) must be captured in the eCRF.

A participant must be withdrawn from study treatment if any of the following stopping criteria are met:

- 1. Liver Chemistry: Meets any of the protocol-defined liver chemistry stopping criteria.
- 2. QTc: Meets any of the protocol-defined stopping criteria.
- 3. Pregnancy: Positive pregnancy test.
- 4. Participant meets at least one of the following criteria for 'loss of asthma control':
 - ACQ-5 score increase from baseline (measured at Visit 2) \geq 0.5 point.
 - Pre-bronchodilator FEV1 decrease from baseline (measured at Visit 2) >7.5 %.
 - Inability to continue inhaled corticosteroid titration which is assessed and determined by the investigator at any time point following randomization, including on scheduled clinic visits.

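### Section 8.1.2: the second bundle-branch-block QTc row has a malformed baseline category, and its relation to the general QTc stopping criteria is not stated

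*Protocol*

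**What the plan says.** Section 8.1.2 of the protocol sets general QTc stopping criteria first: "A participant who meets the bulleted criteria based on the average of triplicate ECG readings will be withdrawn from study treatment". The bullets under that sentence are QTc above 500 msec or uncorrected QT above 600 msec, and "Change from baseline of QTc >60 msec".

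It then turns to a subgroup: "For participants with underlying bundle branch block, follow the discontinuation criteria listed below". Two rows follow:

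- Row 1: "Baseline QTc with Bundle Branch Block <450 msec, Discontinuation QTc with Bundle Branch Block >500 msec".
- Row 2: "Baseline QTc with Bundle Branch Block <450-480 msec, Discontinuation QTc with Bundle Branch Block ≥530 msec".

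Section 8.1 says how stopping criteria combine: "A participant must be withdrawn from study treatment if any of the following stopping criteria are met". Its QTc item is "QTc: Meets any of the protocol-defined stopping criteria".

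The subgroup can be enrolled. Table 2 in Section 6.2 lists as exclusionary "For subjects with complete right bundle branch block: QTc(F) ≥480 msec", so complete right bundle branch block below that limit does not by itself exclude a participant.

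**The concern.** There are two linked problems in a mandatory stopping rule.

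First, row 2 prints its baseline category as an inequality sign in front of a range. That is not well formed. Taken literally, everything up to 480 msec falls under row 2, including the whole of row 1's category, and the two rows carry different thresholds. The same category is printed in the superseded protocol versions bound into the file, so it is probably source text and not a fault of text extraction.

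Second, the section does not say whether the two rows replace the general bullets for these participants or are added to them. The wording that introduces the rows suggests replacement. The general sentence, and the rule in Section 8.1 that any one criterion is enough, make no exception for bundle branch block.

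At stake is whether sites treat identical tracings alike. A stop cannot be reversed, because Section 8.1.3.1 does not allow restart once a Section 8.1 criterion has been met. A missed stop leaves a participant on study treatment against the intended safety rule. In the main analysis, a stop for a reason other than loss of asthma control also sets the primary endpoint to missing (Section 10.4.1). That follows from every such stop, however, and is not special to this defect.

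**Working it through.** The protocol states no computed figure here, so the check is logical. It uses whole-msec values, with baseline QTc from 380 to 480 and on-treatment QTc from 440 to 560. The 380 lower limit is only a bound for counting.

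**Inputs (Sections 8.1 and 8.1.2)**

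| Rule | Baseline | Stop when |
|---|---|---|
| General, absolute | any | QTc >500 |
| General, change | any | QTc − baseline >60 |
| Row 1 | <450 | QTc >500 |
| Row 2 | printed as <450-480 | QTc ≥530 |
| Combination (Section 8.1) | – | any one criterion met |

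**Step 1. Row 2 read literally (every baseline up to 480).** Both rows then apply to baselines 380 to 449, which is 70 values. The rows differ when QTc is above 500 but below 530, that is 501 to 529, which is 29 values. This gives 70 × 29 = 2030 baseline and QTc pairs. Example: baseline 440 with on-treatment 515 meets row 1 (515 >500) but not row 2 (515 <530).

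**Step 2. Row 2 read as the adjacent band 450 to 480, with the sign taken as stray.** No baseline falls in both rows, no pair conflicts, and no baseline from 380 to 480 is left uncovered.

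**Step 3. Apply the any-criterion rule to the two rows alone.** In all 2030 pairs of step 1, row 1 is met, so the outcome is withdrawal. This matches the outcome under step 2. The overlap therefore does not produce two formal outcomes if a site applies both rows and Section 8.1 together. The risk is that a site uses row 2 alone for a baseline below 450.

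**Step 4. Add the general criteria.**

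- Absolute criterion: any QTc ≥530 is also >500. If the general bullet applies to these participants, it is always met before row 2 can be, so row 2 never decides anything. Row 1 then merely repeats the general bullet.
- Change criterion: a change above 60 msec is reached at or below 529 msec when baseline + 61 ≤ 529, that is baseline ≤468. For baselines 450 to 468 this bullet alone would stop treatment before 530 msec.

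**Step 5. Where the unstated relation changes the outcome.** Take baselines 450 to 480 (31 values) with QTc 501 to 529 (29 values): 31 × 29 = 899 pairs. If the rows add to the general criteria, all 899 are stops. If the rows replace them, none is a required stop on QTc. Here the any-criterion rule does not settle the matter, because the question is which criteria belong to the participant in the first place.

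These pair counts describe the rule. They are not numbers of participants.

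**The case against.** A reader might infer that the overlap tells a site to stop and to continue at the same time. The documents do not support that. Both rows are discontinuation criteria, failing to meet row 2 is not an instruction to keep dosing, and Section 8.1 makes one met criterion sufficient. Between the two rows alone, row 1 decides.

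It can also be said that the overlap is a one-character slip. Row 1 already covers baselines below 450, and Table 2 uses limits of 450 and 480 msec, so many readers would take row 2 as the adjacent band, which removes the overlap. That is fair, but it means sites must repair the rule themselves, and it does not answer whether the general bullets apply.

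The affected group is small. Table 2 also lists complete left bundle branch block, and complete right bundle branch block with left fascicular block, among its examples of exclusionary conduction abnormalities. What is left is mainly isolated right bundle branch block, with an on-treatment QTc in a narrow band. This stands.

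Finally, the rhythm findings in the protocol's risk assessment should not be used to enlarge the point. They include four reports of non-sustained ventricular tachycardia, one of them on placebo. The risk text available reports no QT prolongation signal.

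**Conclusion.** The point holds in a limited form. The baseline category in row 2 is malformed and, read literally, overlaps row 1 while carrying a different threshold. Separately, the protocol does not say whether the bundle-branch-block rows replace or supplement the general QTc criteria. If they supplement them, the ≥530 msec row is inoperative. If they replace them, the threshold is fixed by a category that cannot be read as printed.

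The on-treatment band concerned is 501 to 529 msec. For baselines below 450 msec the risk is misapplication only, since the any-criterion rule gives withdrawal. For baselines from 450 to 480 msec the required action itself depends on the unstated relation.

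This rests on whole-msec QTc values and on the reading of Section 8.1 as covering every QTc criterion that applies to the participant. Few participants are likely to be affected, and the documents give no number. No material effect on the efficacy analysis is claimed. No view is taken on which band or threshold is right.

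**What to change.** Reconcile the two bundle-branch-block rows in Section 8.1.2 so that each baseline QTc maps to exactly one row. In the same place, state whether these rows replace the general QTc criteria or apply in addition to them, naming the absolute QTc, uncorrected QT and change-from-baseline bullets. Check that the QTc item in Section 8.1 is consistent with that statement. The bands and thresholds are for the sponsor to decide.

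The cost is one or two lines of protocol wording and a note to sites. It needs no new assessment and no change to sample size or analysis.

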8.1.3. Rechallenge

8.1.3.1. Study Treatment Restart or Rechallenge

Study treatment restart or rechallenge after liver chemistry stopping criteria or any of the individual discontinuation criteria listed in Section 8.1 of the protocol are met is not allowed. Additionally, if hypersensitivity or anaphylactic reaction occurs, infusion should be discontinued and study restart is not allowed.

8.2. Withdrawal from the Study

- A participant may withdraw from the study at any time at his/her own request, or may be withdrawn at any time at the discretion of the investigator for safety, behavioral, compliance or administrative reasons.
 - Note: In order to achieve the stratification balance, as a result of participants' eosinophil count it may be necessary to withdraw participants from the study during the Run-in period.
- If the participant withdraws consent for disclosure of future information, the sponsor may retain and continue to use any data collected before such a withdrawal of consent.
- If a participant withdraws from the study, he/she may request destruction of any samples taken and not tested, and the investigator must document this in the site study records.
- Refer to the SoA for data to be collected at the time of early withdrawal (EW visit) and follow-up and for any further evaluations that need to be completed.

8.3. Lost to Follow Up

A participant will be considered lost to follow-up if he or she repeatedly fails to return for scheduled visits and is unable to be contacted by the study site.

The following actions must be taken if a participant fails to return to the clinic for a required study visit:

- The site must attempt to contact the participant and reschedule the missed visit as soon as possible and counsel the participant on the importance of maintaining the assigned visit schedule and ascertain whether or not the participant wishes to and/or should continue in the study.
- Before a participant is deemed lost to follow up, the investigator or designee must make every effort to regain contact with the participant (where possible, 3 telephone calls and, if necessary, a certified letter to the participant's last known mailing address or local equivalent methods). These contact attempts should be documented in the participant's medical record.
- Should the participant continue to be unreachable, he/she will be considered to have withdrawn from the study with a primary reason of lost to follow-up.

9. STUDY ASSESSMENTS AND PROCEDURES

- Study procedures and their timing are summarized in the Schedule of Activities (SoA) (Section 2).
- Protocol waivers or exemptions are not allowed
- Immediate safety concerns should be discussed with the sponsor immediately upon occurrence or awareness to determine if the participant should continue or discontinue study treatment.
- Adherence to the study design requirements, including those specified in the SoA, is essential and required for study conduct.

No study related procedures may be performed until the informed consent form has been signed by the participant. Selection and modification of the participant's medications prior to study participation is based on the physician's judgment according to sound medical practice, principles, and each participant's needs. A participant's treatment must not be changed merely for the purpose of enabling the participant's participation in the study.

9.1. Efficacy Assessments

The timings of all efficacy assessments are specified in SoA.

9.1.1. Questionnaires

9.1.1.1. Asthma Control Questionnaire ACQ-5

The ACQ-5 measures attributes of asthma control [Juniper, 1999], measured with questions designed to be self-completed by the participant. Participants will complete the ACQ-5 with the use of an e-Diary device on a weekly basis. The ACQ-5 includes five questions (concerning nocturnal awakening, waking in the morning, activity limitation, shortness of breath and wheeze) which enquire about the frequency and/or severity of symptoms over the previous week. The response options for all these questions consist of a zero (no impairment/limitation) to six (total impairment/ limitation) scale. The recall period is the past week. A score of <0.75 indicates well-controlled asthma and a score ≥1.5 indicates poorly controlled asthma [Juniper, 2006]. A change of ≥0.5 in score suggests a clinically important change in score [Juniper, 2005].

9.1.1.2. St. George's Respiratory of Life Questionnaire (SGRQ)

The St. George's Respiratory Questionnaire is a well established instrument, comprising 50 questions designed to measure Quality of Life in patients with diseases of airway obstruction, measuring symptoms, impact, and activity. The questions are designed to be self-completed by the participant [Jones, 1992] with a recall over the past 4 weeks. Higher scores indicate worse health status, and a change of 4 points is considered a clinically relevant change [Jones, 2005].

9.1.2. Daily Diaries

Participants will be issued with a PEF/e-Diary device at Visit 1 for twice daily use (in the morning upon waking and in the evening just before going to bed) throughout the study. The device will be provided by a third-party vendor. Information on the device and its use are documented in the SRM and the third-party vendor manual. Participants will be instructed on how to use the device in order to record results for the following in the eDiary each day from Visit 1 onwards:

- Morning and evening peak flow (best of three).
- Daytime asthma symptom score using a 5-point scale
- Inhalations of rescue medication usage over the previous 24-hours
- Frequency of awakening due to asthma symptoms requiring rescue medication use
- Morning and Evening use of FP/Sal and FP during the run-in and treatment periods

Section 9.1.2 describes the assessments and questionnaires recorded on the eDiary device, as well as the alerts that can be triggered based on recorded results. The data from the eDiary device will be automatically transmitted to a centralized server. The Investigator and designee(s) will be provided with access to the transmitted eDiary data via a vendor-provided portal and should review the data on an ongoing basis to check for the incidence of alerts as well as subject compliance with eDiary use.

Participants will also be issued with a paper Medical Problems/Medications Taken worksheet to record medical problems experienced and medications used during the

study (please refer to the SRM for further details). Participants must also use this paper worksheet to record all healthcare contacts that occur during their participation in the study. This paper worksheet will be used to assist participant recall in discussions with the Investigator, for site staff to then enter as appropriate in the electronic case report form (eCRF).

9.1.2.1. Night-time Awakening, Daytime Asthma Symptom Questions

Every morning upon waking (from the morning after Visit 1 onwards), participants will answer a question on the occurrence of night-time awakenings due to asthma symptoms. The participant's response to the question on the occurrence of night-time awakenings will be either 'Yes' (i.e. Did you wake up due to asthma symptoms (i.e. wheezing, coughing, shortness of breath, or chest tightness) or 'No' (i.e. they did not experience at least one night-time awakening due to asthma symptoms). If 'Yes', participants will be asked to respond either 'Yes' or 'No' to the question on rescue medication (i.e. when you woke up due to your asthma symptoms did you use any rescue bronchodilator?).

On the evening of Visit 1 (just before going to bed) and every evening there-after, participants will answer a question on daytime asthma symptoms. These questions will be answered on a 5-point scale (0 to 4) with '0' representing no daytime asthma symptoms and '4' representing very severe daytime asthma symptoms. Please describe the severity of your asthma symptoms (i.e. cough, wheeze, chest tightness, shortness of breath) today [0=no asthma symptoms, 1=mild asthma symptoms, 2= moderate asthma symptoms, 3=severe asthma symptoms, 4= very severe asthma symptoms].

9.1.2.2. Morning and Evening Home PEF

Participants will conduct PEF measurements using the PEF/eDiary device each morning and each evening. Three measurements for each session will be recorded by the participants in the eDiary. Assessments will be performed:

- After completing all other eDiary assessments
- Prior to albuterol/salbutamol use
- Prior to FP/Sal and FP use

9.1.2.3. Alerts

For safety the following alerts, indicative of worsening asthma, will be programmed into the eDiary with instructions for the participant to contact the investigator and transmit the data to the centralised server as soon as possible if any of the alert criteria are met. An alert in itself will not qualify as a clinically significant exacerbation:

- Decrease in morning PEF ≥30% on at least two of three successive days, compared with Baseline (last 7 days of run-in).
- A daytime symptom score of 3 for at least two of three successive days.
- An increase from baseline of ≥4 puffs /day of albuterol/salbutamol use on 2 consecutive days.

 Awakening due to asthma symptoms requiring rescue medication use for at least two of three successive nights.

If any of the alert criteria are met, email notifications will be sent to the investigator as soon as the data is transmitted to the centralized server. The investigator will make every effort to contact the participants in order to discuss the participants' symptoms and evaluate whether they experienced loss of asthma control.

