Dreading	Pre-	Screen				Tı	reatme	nt Pe	riod				Follow-up Period ²		Period ²	Notes	
Procedure	Screen ing ¹	Run-in	=	Ŀ 2 day	'S				± 3 da	ays			(± 3 days)			Notes	
Visit	0	1	2 ³	3	4	5	6	7	8	9	10	11 (ETP or EW)	12	13	14	1.Pre-screening and screening can occur on the same day 2. FU period to start 4 weeks after ETP or EW visit. 2. Visit 2 = Day 1 (first days of	
Week	-4~-2	-2	0	1	2	4	6	8	10	12	14	16	20	24	28	- 3. Visit 2 = Day 1 (first dose of IP).	
Study Day	-28~-14	-14	1	8	15	29	43	57	71	85	99	113] ⁻ -	
AE/SAE review	X ¹	X1		←===	======>			>	Х	Х	х	At V0 and V1 collect only SAEs considered as related to study participation.					
Concomitant medication review	Х	Х		←====== →				>	Х	Х	Х						
Questionnaires																	
ACQ-5		Х)	X								After randomization, ACQ5 will be completed by the participants every 7 days.	
SGRQ			Χ			Х		Х		Χ		X					
Study Treatment				•			•										
Double blind Study Treatment (IP)			Χ			Х		X		Х						Patients will remain in the clinic for monitoring for at least 2 hours after the end of infusion.	
FP/Sal (500/50) dispensing		Х	Χ														
FP (mcg) dispensing					500	250	100	50									
Dispense albuterol (as needed)		Х	Χ	Х	Х	Х	Х	Х	Х	Х	Х	Х					

SoA Table 2: Timings of PK, target engagement and immunogenicity samples

Dropoduro		Treatment Period									Follow-up ²			Notes
Procedure		± 2 days			± 3 days						(± 3 days)			Notes
Visit	21	3	4	5	6	7	8	9	10	11 (ETP or EW)	12	13	14	1. Visit 2 = Day 1 (first dose of IP). 2. FU period to start
Week	0	1	2	4	6	8	10	12	14	16	20	24	28	4 weeks after ETP or EW visit.
Study Day	1	8	15	29	43	57	71	85	99	113				EVV VISIL.
Double blind Study Treatment (IP)	X			Х		Х		х						
PK sample	X ²	Χ	Χ	X3		X3		X ¹		Х	Х	Χ	Χ	1. Pre dose and post dose. 2. Post dose only. 3. Pre dose only. Pre-dose samples within 2 hours from the planned dosing time. Post-dose samples as soon as possible after end of infusion but must be taken within 4 hours.
Free and total sST2	X ¹	Х	Х	X 3		X_3		X ¹		Х	Х	Х	Х	
Immunogenicit y sample	X ³		Х	X ³		X 3		X ³		Х	Х	Х	Х	

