For participants who discontinue IP early, but have not withdrawn consent to participate in the study, an early withdrawal (EW) visit will be performed 4 weeks after the last dose of blinded study treatment. These participants should continue in the study and complete all assessments at the remaining protocol-defined visits until their EW visit. Participants should resume regular treatment for their asthma, as determined by the investigator. Three Follow-up visits will then be performed 4, 8, and 12 weeks after the EW visit for safety assessments.

Participants who discontinue IP early and withdraw consent to participate in the study should complete as many assessments planned for the EW visit as possible.

Following randomization participants will return to the clinic at least every 2 weeks for scheduled FP dose titration and assessment of asthma control until the last dose of blinded study treatment (Visit 9).

Albuterol/salbutamol will be provided for symptomatic relief to be used on an as needed basis from Screening through to the ETP visit.

The maximum total duration of the study is approximately 33 weeks.

An independent Safety Review Committee (iSRC) will periodically review unblinded safety data to protect and maintain participant safety whilst maintaining scientific validity. Members of the iSRC will be independent of the project. The data will include, but not necessarily be limited to SAEs, Holters, and ECGs. Details are described in the iSRC Charter.

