12.3. Appendix 3: Study Governance Considerations

Regulatory and Ethical Considerations

- This study will be conducted in accordance with the protocol and with:
 - Consensus ethical principles derived from international guidelines including the Declaration of Helsinki and Council for International Organizations of Medical Sciences (CIOMS) International Ethical Guidelines
 - Applicable ICH Good Clinical Practice (GCP) Guidelines
 - Applicable laws and regulations
- The protocol, protocol amendments, ICF, Investigator Brochure, and other relevant documents (eg, advertisements) must be submitted to an IRB/IEC by the investigator and reviewed and approved by the IRB/IEC before the study is initiated.
- Any amendments to the protocol will require IEC/IRB approval before implementation of changes made to the study design, except for changes necessary to eliminate an immediate hazard to study participants.
- The investigator will be responsible for the following:
 - Providing written summaries of the status of the study to the IRB/IEC annually or more frequently in accordance with the requirements, policies, and procedures established by the IRB/EC
 - Notifying the IRB/IEC of SAE or other significant safety findings as required by IRB/IEC procedures
 - Providing oversight of the conduct of the study at the site and adherence to requirements of 21 CFR, ICH guidelines, the IRB/IEC, European regulation 536/2014 for clinical studies (if applicable), and all other applicable local regulations

Financial Disclosure

Investigators and sub-investigators will provide the sponsor with sufficient, accurate financial information as requested to allow the sponsor to submit complete and accurate financial certification or disclosure statements to the appropriate regulatory authorities. Investigators are responsible for providing information on financial interests during the course of the study and for 1 year after completion of the study.

Informed Consent Process

• The investigator or his/her representative will explain the nature of the study to the participant or his/her legally authorized representative and answer all questions regarding the study.

- Participants must be informed that their participation is voluntary. Participants
 or their legally authorized representative will be required to sign a statement of
 informed consent that meets the requirements of 21 CFR 50, local regulations,
 ICH guidelines, Health Insurance Portability and Accountability Act (HIPAA)

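### The daytime-symptom safety alert is set at a score of exactly 3 on a 0–4 scale, so days scored 4 (very severe) do not count as written; it should be ≥3

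*Protocol*

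**What the plan says.** Section 9.1.2.1 has participants rate daytime symptoms every evening on a five-point scale from 0 to 4. Its top two categories are "3=severe asthma symptoms, 4= very severe asthma symptoms".

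Section 9.1.2.3 lists four alerts and introduces them with "For safety the following alerts, indicative of worsening asthma, will be programmed into the eDiary". The daytime-symptom alert reads "A daytime symptom score of 3 for at least two of three successive days". If any alert criterion is met, the participant is told to contact the investigator, the investigator receives an email once the data reach the server, and the investigator tries to contact the participant and judges whether asthma control has been lost.

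Two other alerts in the list carry a numeric threshold, and both are written with an inequality: a morning PEF fall of ≥30%, and an increase of ≥4 puffs per day in rescue use. The fourth alert, awakening that needs rescue medication, is a yes/no item.

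**The concern.** In the daytime-symptom alert, the words for at least apply to the number of days and not to the score. The score is a bare 3 on a scale that goes one step higher, so the worst category does not meet the criterion. The rule then runs backwards at the top of the scale: a participant who goes from two severe days to two very severe days stops meeting it.

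The sentence specifies something to be programmed into a device, and a device does not infer clinical intent. This is also the only one of the four alerts based on daytime symptom severity, and it operates while salmeterol and then fluticasone propionate are being withdrawn. If it was programmed as written, a participant with very severe daytime symptoms could get no prompt from it, and contact with the investigator and recognition of lost control between visits could be delayed.

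**Working it through.** The protocol gives no figure to reproduce here. The check is to compare the rule as written with the rule presumably meant over every possible three-day sequence.

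**Inputs**
- Scale: five values, 0 to 4 (Section 9.1.2.1).
- Rule as written: score = 3 on at least two of three successive days (Section 9.1.2.3).
- Rule presumably meant: score ≥3 on at least two of three successive days.

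**All patterns:** 5³ = 125.

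**Patterns with at least two days ≥3.** Two scores qualify (3, 4) and three do not (0, 1, 2).
- Exactly two qualifying days: C(3,2) × 2² × 3 = 36.
- Three qualifying days: 2³ = 8.
- Total: 36 + 8 = 44.

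**Patterns that fire as written.** One score qualifies (3) and four do not.
- Exactly two days at 3: C(3,2) × 1² × 4 = 12.
- Three days at 3: 1.
- Total: 12 + 1 = 13, all of them among the 44.

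**Silent as written, though at least two days are ≥3:** 44 − 13 = 31, made up of:
- Two or three days at 4: C(3,2) × 4 + 1 = 13. At most one day can then be a 3, so none of these fires.
- One day at 4, one at 3 and one at 0 to 2: 3! × 3 = 18.
- Check: 13 + 18 = 31.

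Direct enumeration by computer gave the same 125, 44, 13 and 31.

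| Three days | As written (= 3) | With ≥3 |
|---|---|---|
| 3-3-0 | fires | fires |
| 3-4-0 | silent | fires |
| 3-4-4 | silent | fires |
| 4-4-0 | silent | fires |
| 4-4-4 | silent | fires |

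The counts weight every pattern equally. The protocol has no data on how often participants would score a 4, so they are not probabilities. They describe this alert alone; any of the other three may still fire on the same days.

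A symbol lost in the PDF conversion is not a plausible explanation. The ≥ signs in the neighbouring bullets survived, and the two superseded protocol versions in the same file carry the same bare 3.

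**The case against.** The strongest reply is that context settles the meaning. The list is headed as safety alerts for worsening asthma, and on an ordered severity scale most readers would take a score of 3 as a threshold. A rule that fires on 3-3-0 and ignores 4-4-4 defeats its own purpose. That is a good argument about intent, and the intent was very probably ≥3. It does not make the written criterion correct, and the written criterion is what a vendor would program and test against.

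Second, any actual harm depends on the vendor's configuration, which is outside the protocol; Section 9.1.2 refers to the study reference manual and the vendor manual for the device. This stands. The wording defect is certain, but a gap in the working device is not.

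Third, there are several backstops:
- The PEF, rescue-use and awakening alerts may fire on the same days, though the protocol does not guarantee it.
- Section 9.1.2 says investigators "should review the data on an ongoing basis to check for the incidence of alerts as well as subject compliance with eDiary use". Sections 3.3.2 and 5.1 have eDiary data sent automatically each day, so a run of 4s can be seen by the site. Part of that review, however, consists of checking for alerts.
- Section 3.3.2 promises participants clear instructions for any increase in symptoms, whether or not an alert fires.
- The Schedule of Activities states "After randomization, ACQ5 will be completed by the participants every 7 days", and Section 5.1 states "Following randomization participants will return to the clinic at least every 2 weeks for scheduled FP dose titration and assessment of asthma control".
- The criteria in Section 8.1 for stopping treatment on loss of control do not use the daytime score.

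These points reduce the likely consequence considerably and also stand. They do not justify leaving the worst symptom category out of a safety rule.

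**Conclusion.** The concern holds. As written, the alert omits the most severe category on its own scale and is silent on 31 of the 44 three-day patterns with at least two days at severe or worse, including every pattern with two or three very severe days. This rests on the literal text of Sections 9.1.2.1 and 9.1.2.3 and on the absence of any statement that a 4 counts. Whether any participant would go without a prompt depends on the vendor's logic, which the protocol does not show.

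The point should be fixed because it is a threshold in a patient-safety rule during controller withdrawal. It is not a threat to the trial's conclusions: the alert is not a component of the primary endpoint, and no bias in that endpoint and no effect on sample size, power or analysis is claimed.

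**What to change.** In the second bullet of Section 9.1.2.3, insert ≥ before the 3, so that a 3 or a 4 counts on each day. All 44 patterns then fire. Check the vendor's programmed logic and its test record against the corrected text, and correct the configuration if it uses equality.

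The cost is a one-symbol correction carried in a protocol amendment and a configuration check. Appendix 3 (Section 12.3) applies to the amendment: "Any amendments to the protocol will require IEC/IRB approval before implementation of changes made to the study design". Design, sample size and analysis stay as they are.
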